## 6.2 EXCLUSION CRITERIA

1. Advanced diabetes complications such as receiving dialysis, registered blind, above ankle amputations.
2. Co-morbid learning difficulties, dementia or current active severe mental illness
3. Lacking the capacity to consent

## 6.3 CONSENT

Written informed consent will be obtained from all study participants in a language they understand before any study procedures are undertaken (enrolment and follow up interviews, blood draws). Local fieldworkers will explain the study and patients through the patient information sheet. The right of the participant to refuse to participate without giving reasons will be respected.

## 6.4 RISKS AND BENEFITS

No major ethical issues are expected since only interventions recommended in established recent guidance issued will be offered. By participating in the study, participants will not be denied any form of care that is currently available to them, subject to local provision of services. Participants may find minor discomfort from the taking blood samples. Trained phlebotomists will take the blood sample. Results of Interim blood test, that is not part of routine care, such as HbA1c will be fed back by the study team to health care professionals only if there is a need for additional clinical treatment/management. The information sheet will stress the independence of the research team and that all data will be anonymised

The Patient Information Sheet will provide potential participants with information about the possible benefits and anticipated risks of taking part in the study either as a participant in the main intervention or in the qualitative study. Participants will be given the opportunity to discuss any issues with their healthcare provider or researcher prior to consenting to participate. The researcher will inform the participant if new information comes to light that may affect the participant's willingness to participate in the study.

## 6.5 WITHDRAWAL CRITERIA

Participants have the right to withdraw from the study at any time for any reason. It is understood by all concerned that an excessive rate of withdrawals can render the study uninterpretable; therefore, unnecessary withdrawal of patients should be avoided. Should a patient decide to withdraw from the study, all efforts will be made to report the reason for withdrawal as thoroughly as possible. Should a patient withdraw from study intervention only, efforts to continue to obtain follow-up data will be made, with the permission of the patients. Patients will be asked if they are willing to be contacted by a researcher at 6 and 12 months and if not whether the study is able to collect ongoing data from their medical records.

# 7. INTERVENTION

## 7.1 INTERVENTION DESCRIPTION AND DELIVERY

The intervention will consist of four Work packages (WPs):

**WP 1: Professional development of nurses and village health volunteer (VHVs) to educate diabetes patients on self-management.**

a. Mapping of the knowledge from a desktop reviews and focus groups from nurses and VHVs to develop a paper prototype of the intervention, including its hypothesised pathways of action (e.g. common-sense model of illness, empowerment, discovery learning, social learning, and social support) and a training manual for nurses and health volunteers.

b. Development of 6 brief films (5-6 minutes long) to trigger discussions on key topic areas during structured periods of the intervention meetings, and a longer film to be used a training resource for nurses and village health volunteers. There is an increasing recognition that films are a highly efficient medium for communicating large amounts of information with a better recall, particularly in low literacy settings. Short films can be used to challenge existing beliefs to support behaviour change and create a connection within viewer groups to catalyse support. Films will be developed using an established theory-based process, which uses participatory approaches to ensure that films meet the cultural, psychological, and contextual constructs of the audience. Films will be in local language and use local actors.

**WP 2: Piloting trial protocol and intervention of the structured diabetes self-management education programme for people with newly diagnosed and those with poor control of their diabetes within three years of diagnosis plus carers**

We will pilot the intervention at four community hospitals. The pilot will not be a smaller version of the trial; instead, several independent studies will be carried out, mainly to refine the intervention. We will also collect some preliminary data to check our assumptions and processes for the trial. The intervention modules will be tested with two nurses and village health volunteers each, who will be trained to deliver them to groups of 10-20 persons with diabetes and their carers. Several modules will be tested in parallel, as they will be designed to be standalone. Data on 'what works, doesn't work, and what more needs to be added' for each session will be collected using a) ethnographic methods, involving direct observations of the sessions, which will be video recorded, and unstructured and semi-structured interviews (24 in total, purposively sampled), and b) focus group discussions, with the nurses, village health volunteers, and group participants (8 in total). The intervention modules will be refined using participatory research methodology, and following an iterative process, including piloting, feedback, analysis, reflection, and modification, until the sessions are fit for purpose. We will collect quantitative data on at least 100 consecutive persons with diabetes attending the four community hospitals (i.e. 25 at each site), and semi-structured interviews on a subsample of ~20 people, to document the current care processes, collect data on distribution of outcome measures to confirm our sample size calculations, and pilot the trial organization and study instruments, as not all have been previously used in Thai populations.

**WP 3: Main trial evaluation on structured DSME for people with newly diagnosed with type 2 diabetes and those with poor control of their type 2 diabetes within three years of diagnosis and their carers.**

The intervention will be evaluated in primary care networks in Chiang Mai and Lampang province in northern Thailand. While diabetes is diagnosed at tertiary hospitals, it is managed at community hospitals and health centres, which are served by a full-time nurse (doctor visits weekly), and 10-15 village health volunteers linking patients in the community. A 3-arm cluster randomized trial with inbuilt process and economic evaluation will be carried out (see Annexe for trial flow diagram). The 21 primary care units will be randomized (seven each) to provide nurse-led DSME, peer-led DSME, or standard care. Randomisation will be minimised by primary care networks to account for any variation in practice, although this is expected to be small because it is determined by the tertiary care hospital, which is same for both. The nurses and village health volunteers in intervention arms will be trained to deliver the intervention (at the community hospital or neighbourhoods as appropriate) using training films. No changes will be made to standard care, which currently involves a brief didactic educational session at the time of diagnosis of diabetes. Process evaluation will aim to assess intervention delivery (fidelity, dose and reach), clarify causal mechanisms (those hypothesised by theory of change developed within the project or identify unexpected ones), and identify contextual factors (barriers, facilitators) associated with variation in outcomes. Data for economic evaluation (resource usage and quality of life using EQ-5D) will be obtained prospectively alongside the trial.

#### WP 4: Health systems analysis to identify best policy options

Using ideas from existing literature on the subject as a basis, we will undertake targeted interviews with Thai policy makers to jointly define a scalability construct of relevance to them and create a framework for operationalising it. Relevant data from policy documents and available databases will be collected to undertake health system analyses. Key criteria for assessment of scalability are likely to include, among others: a) cost-effectiveness and affordability (i.e. the total cost to government of scaling up the intervention, and this cost in relation to total health budget, as these metrics may be of more interest to policy makers); b) acceptability of the intervention to users and providers, with a particular focus on integration of the new activity in the existing workload and health information systems; and c) compatibility of the new intervention with existing policy frameworks, although this will also be taken into consideration while developing the intervention. Our preliminary conversations with Thai policy makers suggest a strong interest in using DSME to improve skills of frontline workers in behavioural interventions, which could then be transported to other chronic disease interventions, suggesting that capacity building benefits may be an important consideration in policy makers' decision.

## 8. ASSESSMENT AND FOLLOW-UP

Each participant will be involved in the study for a minimum of 12 months after taking consent and baseline data. However, there may be a delay in contacting and scheduling participants for follow ups therefore, this may be slightly longer. The study is expected to start October 2018 and finish September 2021.

a. Questionnaire data will be collected by field workers via in-person interview for the full sample at baseline, 6 and 12 months at the community hospital where they were recruited (Table 1). A custom-designed form linked to Microsoft Access will be used to collect, validate, verify, and store respondents' data where possible or else data will be collected via paper forms and double-entered into the databases. All data files and databases will be password protected.

b. Biological samples. Blood samples will be collected from participants at baseline, 6 and 12 months, to measure Blood glucose, HbA1c and lipids, coordinating where possible with the annual routine tests offered to patients to reduce duplication. Blood will be drawn by a trained phlebotomist when participants come for interview and sent to laboratory for analysis. Data will be linked to the participant information using a unique respondent ID, which will be assigned to all study participants.

c. Interviews. During intervention development and qualitative evaluation, a subset of participants will be followed up using in-depth interviews and focus group discussions. These will be recorded on digital Dictaphones, with recordings initially stored on a personal computer or laptop in an encrypted folder with password protection. Recordings will be transcribed by professional transcribers conditional on signing of confidentiality and nondisclosure agreements.

**Table 1: Questionnaire-based outcome measures**

Target domain	Questionnaire	Adapted for Thailand	Validated in Thailand
Quality of life	WHOQOL	Yes	Yes 
	EQ-5D	Yes	Yes 
Depression	Hospital Anxiety and Depression Scale (HADS)	Yes	Yes 
	Perceived stress questionnaire	Yes	Yes 
Physical activity	International Physical Activity Questionnaire	Yes	Yes 
Diabetes knowledge and skills	Brief diabetes illness perception questionnaire	Yes	Yes 
	Diabetes Self-Management Education and Support (DMSES)	Yes 	No
	Summary of Diabetes self-care activities questionnaire (SDSCA)	Yes	Yes 
Satisfaction with intervention	Chronic Illness Resources survey	Yes	Yes 

### 8.1 LOSS TO FOLLOW UP

The field team shall hold weekly briefs preferably on Friday mornings with the Study Co-ordinators to generate a list of priority areas and lost to follow up (LTFUP) participant lists. Arrangements to follow up participants who have not turned up for their appointment will be made. Participants will be sent text message reminders prior to their appointment. If they fail to show, then they will be contacted by phone or by home visit if phoning is not possible to understand the reasons and reschedule another appointment within a week. They will be declared lost to follow-up if they do not show for a month and are untraceable.

## 9. STATISTICS AND DATA ANALYSIS

The total number of participants estimated to be involved in the study is 693. Approximately 60 semi-structured interviews will be conducted throughout the course of the project (including intervention development, piloting and process evaluation), as well as 15-20 focus group discussions and 20 ethnographic observations.

### 9.1. SAMPLE SIZE CALCULATION

This study was powered to detect a clinically important difference of 0.6 units HbA1c (SD 1.5 units) between the control and intervention arms. We required 693 participants from 21 hospitals (7 per arm) to achieve 80% power at 2.5% significance level (to account for multiple testing), assuming an ICC between hospitals of 0.02 and loss to follow-up rate of 20%.

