## 4. STUDY DESIGN

### 4.1 DESCRIPTION OF THE STUDY DESIGN

This is a four Workstream (WS) programme design based in Thailand aimed at improving cardiovascular risk and control of blood glucose among people with diabetes.

**WS1 and WS2:** Intervention development (content and delivery model) for DSME.

**WS3 and WS4:** A 3-arm cluster randomised trial in primary care units with an inbuilt process and economic evaluation. Twenty-one primary care units will be randomized (seven each) to provide nurse-led DSME, peer-led DSME, or standard care. People with diabetes are the units of analysis. The trial will be unblinded.

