## 10.2. DATA ANALYSIS

### 10.2.1 QUANTITATIVE ANALYSIS

Available outcome data will be analysed on an intention to treat basis. Potential clustering of outcomes at the level of community hospitals will be accounted for using mixed-effects models. Adjustment for baseline imbalances in outcomes or relevant covariates will be considered as appropriate. Effects of variations in intervention uptake and other relevant effect modifiers will be explored.

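### Section 9.1 makes no allowance for estimating between-unit variance from seven units per arm: an unadjusted test with valid degrees of freedom has about 75% power for 0.6, not 80%

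*Combined protocol and SAP*

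**What the plan says.** Section 4.1 sets the unit of randomisation: "Twenty-one primary care units will be randomized (seven each) to provide nurse-led DSME, peer-led DSME, or standard care". Section 9.1 says the study was "powered to detect a clinically important difference of 0.6 units HbA1c (SD 1.5 units) between the control and intervention arms" and continues: "We required 693 participants from 21 hospitals (7 per arm) to achieve 80% power at 2.5% significance level (to account for multiple testing"). It assumes an ICC of 0.02 and 20% loss to follow-up. It prints no formula, does not say whether the 2.5% is one- or two-sided, and does not say whether 1.5 is the SD at 12 months, of change, or after adjustment for baseline.

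On analysis, section 10.2.1 says: "Potential clustering of outcomes at the level of community hospitals will be accounted for using mixed-effects models". It names no degrees-of-freedom or small-sample method. It then says: "Adjustment for baseline imbalances in outcomes or relevant covariates will be considered as appropriate". Baseline HbA1c will be available in any case, because section 8 provides that "Blood samples will be collected from participants at baseline, 6 and 12 months, to measure Blood glucose, HbA1c and lipids". The pilot in section 7.1 (WP 2) is meant to "collect data on distribution of outcome measures to confirm our sample size calculations".

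**The concern.** Units, not people, are randomised, so each comparison of an intervention arm with control is judged against variation between units. That variation has to be estimated from 21 units in three arms, or from 14 if each comparison is modelled separately. A design-effect calculation inflates the sample size for the ICC but then refers the test to a normal distribution, or to a t distribution with individual-level degrees of freedom. With seven units per arm the difference matters: the two-sided 2.5% critical value is 2.24 for the normal, 2.45 on 18 degrees of freedom and 2.56 on 12.

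HbA1c is co-primary (section 4.1.1), and 0.6 is the difference the plan itself calls clinically important. Section 10.2.1 does not fix the reference distribution, so it is open whether the stated power or the stated significance level will fail. It also means that this choice, and the choice of whether to adjust for baseline, could be made after the results are seen.

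**Working it through.** **Inputs (section 9.1).** Difference 0.6, SD 1.5, power 80%, significance level 2.5%, ICC 0.02, seven units per arm, 20% loss, 693 recruited. That is 693/21 = 33 recruited and 33 × 0.8 = 26.4 evaluable per unit. Equal unit sizes are assumed.

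**Reproducing 693.**
- Individually randomised n per arm = 2(2.2414 + 0.8416)² × (1.5/0.6)² = 118.8.
- Evaluable per unit, m, solves 7m/(1 + (m − 1) × 0.02) = 118.8, so m = 118.8 × 0.98/(7 − 118.8 × 0.02) = 25.18, rounded up to 26.
- 26/0.8 = 32.5, rounded up to 33; 33 × 21 = **693**.
- An individual-level t calculation (120.1, up to 121; m = 25.89, up to 26) also gives 693.
- One-sided 2.5% gives n = 98.1, m = 19.09 (up to 20), 25 recruited per unit and 525 in all.

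The plan therefore used a two-sided test with no allowance for the number of units. This is inferred from the match, since no formula is printed.

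**Power at 693, unadjusted.** SE = 1.5 × √[(2/7)(0.02 + 0.98/26.4)] = 0.1916, so 0.6/0.1916 = 3.131. The t rows use the noncentral t distribution with that noncentrality.

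| Reference | Critical value | Power | Difference detectable at 80% power |
|---|---|---|---|
| Normal | 2.241 | 81.3% | – |
| t, 18 df (21 units − 3 arms) | 2.445 | 74.8% | 0.636 |
| t, 12 df (14 units − 2 arms) | 2.560 | 71.1% | 0.662 |

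A simulation of unit-mean t-tests, with unit sizes drawn as Binomial(33, 0.8), gave 74.4% (18 df) and 70.9% (12 df).

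**What a mixed model would do.** Simulated balanced REML with the between-unit variance truncated at zero (12 million draws each). The Satterthwaite-type rule uses between-unit df if the variance estimate is positive and residual df if it is zero.

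| Model | Reference | Type I error | Power |
|---|---|---|---|
| Three-arm | Normal | 3.3% | 80% |
| Three-arm | Satterthwaite-type | 2.4% | 75% |
| Two-arm | Normal | 3.5% | 80% |
| Two-arm | Satterthwaite-type | 2.4% | 71% |

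Without truncation, the chance that a t statistic exceeds 2.241 in absolute value is 3.8% on 18 df and 4.5% on 12.

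**Dependence on the ICC.** At 0.01, power is 88% (normal), 83% (18 df) and 80% (12 df). At 0.03 it is 74%, 67% and 64%. Power on 18 df reaches 80% only if the ICC is 0.0135 or lower.

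**Effect of adjusting for baseline HbA1c.** The correlation r between baseline and 12-month HbA1c is not in the documents, so the values are assumptions. Baseline is also assumed to explain the same share of both variance components. Power on 18 df:

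| Meaning of SD 1.5 | Residual SD | r = 0.4 | r = 0.5 |
|---|---|---|---|
| Unadjusted 12-month SD | 1.5√(1 − r²) | 82% | 87% |
| SD of change | 1.5√((1 + r)/2) | 89% | 87% |
| Already a residual SD | 1.5 | 75% | 75% |

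Under the first meaning, 80% needs r of about 0.33, or 0.41 if only the within-unit variance falls. On 12 df the figures are 79% at r = 0.4 and 84% at r = 0.5.

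**The case against.** The strongest reply is that nothing in section 9.1 is miscalculated. The printed inputs give 693, clustering is allowed for, and the 75% applies only if the investigators decline an adjustment that section 10.2.1 leaves open and for which they will hold the data. A modest correlation of about 0.33 would restore 80% on 18 df. The loss is also no larger than what a shift in the ICC from 0.02 to 0.01 or 0.03 would cause, and a pilot is planned to check the inputs.

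The arithmetic is indeed sound for the method used. The fault is that the method does not match a seven-units-per-arm analysis. An adjustment that is merely possible cannot support a stated power, and adjustment alone does not correct the type I error of a normal reference. The pilot looks at outcome distributions, not degrees of freedom.

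Two qualifications stand. First, 75% and 0.64 for an unadjusted 12-month comparison take 1.5 as the 12-month SD, which is the natural reading of "0.6 units HbA1c (SD 1.5 units") but is not stated. If it were the SD of change (equal SDs at both times), unadjusted power on 18 df would be 83% at r = 0.4 and 64% at r = 0.6. If it were a residual SD, it would be 67% at r = 0.4 and 61% at r = 0.5. Second, section 5 minimises by primary care network. Adding that factor to the model would cost about one degree of freedom if there are two networks, giving 74.4% on 17 df. That does not change the conclusion.

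**Conclusion.** The concern holds. At the plan's own inputs, an unadjusted analysis cannot deliver both 80% power and the 2.5% level. With valid degrees of freedom, the chance of missing a true difference of 0.6 is about 25% rather than 20% (29% if the comparisons are modelled pairwise). With a normal reference, the error rate that was tightened for multiple testing is exceeded by about a third (3.3% against 2.5%).

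These figures assume a two-sided test, 1.5 as the unadjusted 12-month SD, an ICC of 0.02, 26.4 evaluable per unit and equal unit sizes. The figure of 75% takes one three-arm model, which is the more natural reading of sections 4.1 and 10.2.1 and the more favourable one. The point should be fixed, but it does not call for a larger trial.

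**What to change.** **Section 10.2.1.** Specify one three-arm linear mixed model for 12-month HbA1c, with a random intercept for primary care unit and fixed effects for arm and baseline HbA1c. Test each intervention arm against control with a named small-sample method; Kenward-Roger, Satterthwaite or between-cluster degrees of freedom would each serve. For baseline HbA1c this replaces the discretionary wording. State also whether the minimisation factor is in the model.

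**Section 9.1.** State that the test is two-sided and say what SD 1.5 refers to. Then do one of the following:
- If 1.5 is the unadjusted 12-month SD, restate the unadjusted power for 0.6 as about 75%, or the difference detectable at 80% power as about 0.64.
- Quote power for the adjusted analysis with the assumed correlation written out. An example is about 82% at r = 0.4 on 18 df (79% on 12 df), valid only if 1.5 is the unadjusted 12-month SD and baseline explains the same share of both variance components.

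If 1.5 turns out to be an SD of change or a residual SD, recompute the figures before printing them.

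**Cost.** Text in two sections, a less favourable stated unadjusted power, and slightly more analysis work. No participants, units, visits or blood tests are added. For comparison, reaching 80% unadjusted on 18 df by enlarging the trial would need m = 31.8, up to 32 evaluable per unit; 32/0.8 = 40 recruited; 40 × 21 = 840 in all. That is not proposed.

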## 6. SELECTION AND WITHDRAWAL OF PARTICIPANTS

All new referrals for diabetes management and those having difficulties managing their diabetes the first three years of diagnosis at the 21 primary units over a 6-month period (N=693) will be recruited to the trial, and offered intervention determined by the trial arm. Prospective participants will be made aware of the study through posters and information sheets. All new referrals will be invited to take part. Local fieldworkers will visit the hospitals and obtain informed consent for study participation. Once consent has been provided, participants will be asked to complete a short questionnaire and to give contact details.

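### The 80% power in section 9.1 assumes 21 equal units of 33 and a normal approximation, and makes no allowance for the unequal unit sizes that section 6 will produce

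*Combined protocol and SAP*

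**What the plan says.** Section 9.1 describes the trial as "powered to detect a clinically important difference of 0.6 units HbA1c (SD 1.5 units) between the control and intervention arms". The total is given as "We required 693 participants from 21 hospitals (7 per arm) to achieve 80% power at 2.5% significance level", with the remaining inputs stated as "assuming an ICC between hospitals of 0.02 and loss to follow-up rate of 20" per cent. It gives no variation in unit size, does not mention unequal units, and does not say whether the calculation used a normal or a t reference.

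Section 6 sets the recruitment rule: new referrals, and people having difficulty managing their diabetes within three years of diagnosis, "at the 21 primary units over a 6-month period (N=693) will be recruited to the trial". No quota or cap per unit is stated. Section 5 allocates seven units to each arm. Section 10.2.1 plans mixed-effects models for the clustering, names no degrees-of-freedom method, and leaves baseline adjustment to be considered as appropriate.

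**The concern.** The total divides exactly into 21 units of 33, which points to a calculation with equal units. The recruitment rule does not deliver equal units: with a common six-month window and everyone eligible invited, each unit's size follows its own patient volume. For a fixed total, variation in cluster size can only reduce the precision of a between-cluster comparison, so the stated power belongs to a more favourable design than the one described.

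What is at stake is the reliability of the 80% figure for co-primary outcome 1 (HbA1c). A null result would be read against that figure. The same calculation also appears to rest on a normal approximation with only seven units per arm, so restating it for unequal size while keeping that approximation would leave the larger part of the optimism in place.

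**Working it through.** **Inputs from section 9.1:** difference 0.6, SD 1.5, power 80%, significance 2.5%, ICC 0.02, loss 20%, 7 units per arm, total 693. Sidedness is not stated; two-sided is taken because it reproduces the total.

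**Step 1: reproduce 693.**
- Unclustered n per arm = 2 × [1.5 × (2.241 + 0.842) / 0.6]² = 118.8, that is 119.
- Evaluable per unit with 7 equal units: m = n(1 − ICC) / (7 − n × ICC) = 118.8 × 0.98 / (7 − 2.376) = 25.2, rounded up to 26.
- Recruited per unit: 26 / 0.8 = 32.5, rounded up to 33.
- Total: 33 × 21 = 693, exact.

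The other readings tried do not fit. One-sided 2.5%, or two-sided 5%, gives 525. A design effect based on 33 per unit gives about 732.

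**Step 2: power at equal size.** Evaluable per unit is 33 × 0.8 = 26.4, or 184.8 per arm.
- Design effect = 1 + 25.4 × 0.02 = 1.508.
- SE = √(2 × 1.5² × 1.508 / 184.8) = 0.1916, and 0.6 / 0.1916 = 3.131.
- Power = Φ(3.131 − 2.241) = 81.3%.

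Rounding up therefore leaves about 1.3 points of slack.

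**Step 3: unequal size.** The CV is not in the documents, so a range is shown. For a mixed-model analysis, the efficiency relative to equal units is approximately 1 − CV² × L(1 − L), with L = m × ICC / (m × ICC + 1 − ICC) = 0.528 / 1.508 = 0.350 and L(1 − L) = 0.2275. The ratio 3.131 is multiplied by the square root of this efficiency. The last column uses the more conservative design effect 1 + ((1 + CV²)m − 1) × ICC.

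| CV | Efficiency | Ratio | Power, mixed model, normal | Power, conservative design effect, normal |
|---|---|---|---|---|
| 0 | 1.000 | 3.131 | 81.3% | 81.3% |
| 0.3 | 0.980 | 3.099 | 80.4% | 80.0% |
| 0.5 | 0.943 | 3.041 | 78.8% | 77.7% |
| 0.7 | 0.889 | 2.951 | 76.1% | 74.3% |

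Power reaches 80% at a CV of about 0.37 with the mixed-model efficiency and about 0.30 with the conservative design effect. A simulation drawing gamma-distributed unit sizes and using the exact mixed-model information gave mean power of 80.4% at CV 0.3 and 78.7% at CV 0.5, in line with the approximation.

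**Step 4: t reference.** With 21 units in three arms, 21 − 3 = 18 df is assumed. The critical value rises from 2.241 to 2.445. Power from the noncentral t, with the same ratios:

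| CV | 18 df | 12 df (two arms only, 14 − 2) |
|---|---|---|
| 0 | 74.8% | 71.1% |
| 0.5 | 72.1% | 68.3% |
| 0.7 | 69.2% | 65.5% |

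**Step 5: separate the two causes** at CV 0.5 and 18 df. The t reference alone costs 81.3 − 74.8 = 6.5 points at equal size. Unequal size then costs 74.8 − 72.1 = 2.7 points.

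**The case against.** The strongest reply is that no shortfall from unequal size has been shown. The documents give no CV, the rounding slack absorbs a CV up to about 0.37 under the planned analysis, and at CV 0.5 power is only 1.2 points under 80% on the normal approximation. That is small beside the uncertainty in the SD, ICC and loss rate. This stands. A reader might infer from the recruitment rule that unequal units by themselves put power below 80%. The documents do not support that, because the result depends on a CV they do not contain.

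A reader might also attribute the whole fall to the low seventies to unequal size. That is not supported either: Step 5 shows that most of it comes from the small number of units, and it would occur with units of exactly 33. The 18 df are an assumption too, as section 10.2.1 names no method.

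Baseline adjustment could recover the loss. HbA1c is measured at baseline (section 8), and the calculation takes no credit for it. With an assumed baseline-to-outcome correlation of 0.5, scaling the SD by √(1 − 0.5²), power at CV 0.5 would be about 90% (normal) or 85% (18 df). At a correlation of 0.3 it would be about 83% or 76%. This is a fair mitigation, but section 10.2.1 does not commit to adjustment and the documents give no correlation.

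Finally, the pilot described in section 7.1 is meant to confirm the sample size calculation. It does so through the distribution of outcome measures, at four sites with 25 people each, so it will not supply the variation in unit size.

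**Conclusion.** The point holds as an omission in section 9.1. The stated 80% rests on equal units and a normal approximation, while section 6 makes unequal units the expected result, and no allowance is made. The effect of size variation alone is modest and conditional: none of consequence up to a CV of about 0.37 (0.30 on the conservative formula), then 78.8% at 0.5 and 76.1% at 0.7. With a t reference on 18 df, power is below 80% whatever the CV, at 74.8%, 72.1% and 69.2% for CV 0, 0.5 and 0.7, and the few units account for most of that at moderate CV.

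These figures rest on two-sided 2.5%, the plan's own SD, ICC and loss rate, an assumed CV range, assumed degrees of freedom, and no credit for baseline adjustment. The point does not show that 693 is unworkable. It shows that the stated power should be recalculated for the design as written.

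**What to change.** In section 9.1, obtain the CV of unit size from six-month referral counts at the 21 units, state it, and recompute power for 693 using the mixed-model efficiency and a t reference with a named degrees-of-freedom method. Then replace the 80%. On the plan's inputs this would read about 72% at an assumed CV of 0.5 on 18 df, before any credit for baseline adjustment. If credit is to be claimed, adjustment for baseline HbA1c has to be prespecified in section 10.2.1 and the assumed correlation stated.

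A recruitment target of 33 per unit is not recommended on this ground. It would change the fixed-window, all-eligible recruitment of section 6 for a gain of only a few points.

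The cost is a less favourable stated power and the work of collecting referral counts. Recruitment is unaffected.
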